### **10.6 Protocol Exceptions and Deviations**

No prospective entry criteria protocol deviations are allowed; all subjects must meet all eligibility criteria in order to participate in the study.

Protocol waivers for eligibility and use of prohibited medication during the study (Section 4.5.1) will not be granted by the Sponsor under any circumstances. If, during the course of a subject's participation in the trial it is discovered that the subject did not meet all eligibility criteria, he or she will be discontinued, unless the discontinuation presents an unacceptable medical risk. The justification to allow the subject to continue in the trial will be made by the Sponsor, with medical input from the Investigator, and will be documented. If allowed to remain in the trial, this will be reported as a major protocol deviation and not a waiver. All follow-up safety assessments must be completed and documented in [REDACTED] Section 6.3.9, [REDACTED] protocol deviation to the Sponsor and, if required, to the IRB/EC in accordance with local regulatory [REDACTED] [REDACTED]

### **10.7 Protocol Amendments**

Changes to the protocol may be made only by the Sponsor (with or without consultation with the Investigator). All protocol modifications must be submitted to the site IRB/EC in accordance with local requirements and, if required, to Regulatory Agencies, as either an amendment or a notification. Approval for amendments must be awaited before any changes can be implemented, except for changes necessary to eliminate an immediate hazard to trial

subjects, or when the changes involve only logistical or administrative aspects of the trial. No approval is required for notifications.

## **11 STUDY MONITORING, AUDITING, AND INSPECTING**

### **11.1 Quality Control and Quality Assurance**

The Sponsor or designee and Regulatory Agency inspectors are responsible for contacting and visiting the Investigator for the purpose of inspecting the facilities and, upon request, inspecting the various records of the trial (e.g., eCRFs and other pertinent data) provided that subject confidentiality is respected.

The Sponsor's or designee's monitor is responsible for inspecting the eCRFs at regular intervals throughout the study to verify adherence to the protocol; completeness, accuracy, and consistency of the data; and adherence to local regulations on the conduct of clinical research. The monitor should have access to subject medical records and other study-related records needed to verify the entries on the eCRFs.

The Investigator agrees to cooperate with the monitor to ensure that any problems detected in the course of these monitoring visits are resolved.

In accordance with ICH Guidance on GCP and the Sponsor's audit plans, a certain percentage of sites participating in this study will be audited. These audits may include a review of site facilities (e.g., pharmacy, drug storage areas, and laboratories) and review of study-related records may occur in order to evaluate the trial conduct and compliance with the protocol, ICH Guidance on GCP, and applicable regulatory requirements.

The Sponsor's or designee's representatives, Regulatory Agency inspectors, and IRB/EC representatives who obtain direct access to source documents should also respect subject confidentiality, taking all reasonable precautions in accordance with applicable regulatory requirements to maintain the confidentiality of subjects' identities.

#### **12.1 Ethical Standard**

The study will be conducted in compliance with the protocol, the Declaration of Helsinki, ICH GCP, and other applicable regulatory requirements.

The study will be performed in accordance with Health Insurance Portability and Accountability Act (HIPAA) regulations, US FDA GCP Regulations (US CFR 21 parts 50, 54, 56, and 312), and ICH Guidance on GCP (E6) and clinical safety data management (E2A).

In accordance with Directive 75/318/EEC, as amended by Directive 91/507/EEC, the final clinical study report will be signed by an Investigator and/or Coordinating Investigator who will be designated prior to the writing of the clinical study report.

## **12.2 Institutional Review Board/Ethics Committee**

The Investigator or designee will provide the IRB/EC with all requisite material, including a copy of the protocol, informed consent, and any subject information or advertising materials. The study will not be initiated until the IRB/EC provides written approval of the protocol and the informed consent and until approved documents have been obtained by the Investigator and copies received by the Sponsor. All amendments will be sent to the IRB/EC for information (minor amendment) or for submission (major amendment) before implementation. The Investigator will supply the IRB/EC and the Sponsor with appropriate reports on the progress of this study, including any necessary safety updates, in accordance with the applicable government regulations and in agreement with policy established by the Sponsor.

## **12.3 Informed Consent Process**

Properly executed, written informed consent must be obtained from each subject prior to any screening procedures.

The informed consent must, at a minimum, include the elements of consent described in the ICH Guidance on GCP and the US CFR 21 part 50.25. A copy of the ICF planned for use will be reviewed by the Sponsor or designee for acceptability and must be submitted by the Investigator or designee together with the protocol, to the appropriate IRB/EC for review and approval prior to the start of the study at that investigational site. Consent forms must be in a language fully comprehensible to the prospective subject. The Investigator must provide the Sponsor or designee with a copy of the IRB/EC letter approving the protocol and the ICF before the study drug supplies will be shipped and the study can be initiated [REDACTED]

The consent form must be revised if new information becomes available during the study that may be relevant to the subject. Any revision must be submitted to the appropriate IRB/EC for review and approval in advance of use. [REDACTED]

### **12.3.1 Consent and Other Informational Documents Provided to Subjects**

The subject must be given a copy of the signed informed consent and the original maintained in the designated location at the site.

### **12.3.2 Consent Procedures and Documentation**

It is the Investigator or designee's responsibility to obtain written informed consent from the subject after adequate explanation of the aims, methods, anticipated benefits, and potential

hazards of the study. The subject must be given ample time to decide about study participation and opportunity to inquire about details of the study. The IRB/EC-approved consent form must be personally signed and dated by the subject and by the person who conducted the informed-consent discussion. The Investigator or appropriate site personnel must document the details of obtaining informed consent in the subject's study documents.

Copies of signed forms must be given to the signatories and original forms must be maintained in the designated location at the site.

### **13 PUBLICATION PLAN**

All publication rights are delineated in the Clinical Study Agreement and/or other separate agreements with the Investigator and/or Institution, as applicable.

### **14 CONFLICT OF INTEREST POLICY**

#### **14.1 Finance, Insurance, and Indemnity**

Arrangements for finance, insurance and indemnity are delineated in the Clinical Study Agreement and/or other separate agreements with the Investigator and/or Institution, as applicable.

[REDACTED]

## 16 APPENDICES

### Appendix A Prohibited and Restricted Medications

Subjects taking prohibited medications at study entry will not be eligible for the study. Subjects taking prohibited medications during the trial will be discontinued, unless the discontinuation presents an unacceptable medical risk. The justification to allow the subject to continue in the trial will be made by the Sponsor/Medical Monitor with medical input from the Investigator, and will be documented. If allowed to remain in the trial, this will be reported as a major protocol deviation and not a waiver.

The table below lists prohibitions and restrictions by medication class, including representative medications within class. Medications within each class include but are not limited to the examples listed in this table. Any questions regarding prohibited and restricted medications should be discussed with the Medical Monitor or appropriate designee.

Medication Class	Medication a	Prohibition/restrictions
Antipsychotics other than pimavanserin	PROHIBITED 
 
All in class
 
	
 
Must be washed out 2 weeks or 5 half-lives (whichever is longer) prior to Baseline
 
All antipsychotics are prohibited
 

Anticholinergics	PROHIBITED 
 
Centrally acting anticholinergics                             
 
benztropine
 
biperiden
 
trihexiphenidyl
 
oral diphenhydramine
 
 
 
	
 
Centrally acting anticholinergic medications are prohibited and should be washed out and discontinued at least 2 weeks or 5 half-lives (whichever is longer) prior to Baseline
 

	UNRESTRICTED 
 
Peripherally acting anticholinergics
 
Topical diphenhydramine
 
	
 
Peripherally acting anticholinergic medications and topical diphenhydramine are allowed without restriction
 

Anticonvulsant and mood stabilizers	PROHIBITED 
 
carbamazepine
 
lamotrigine
 
lithium
 
phenytoin
 
	
 
Must be washed out prior to Baseline or for 5 half-lives of the drug
 
Prohibited throughout the study
 

	RESTRICTED 
 
valproate
 
	
 
Valproate may be used if dose unchanged for at least 4 weeks prior to Baseline and dose should be expected to remain unchanged until the subject's final visit.
 

Antidepressants other than background therapy	PROHIBITED 
 
mirtazapine
 
nefazadone
 
fluvoxamine
 
	
 
Prohibited throughout the study
 
Must be discontinued at least 2 weeks or 5 half-lives (whichever is longer) prior to the Baseline visit
 

Medication Class	Medication a	Prohibition/restrictions
	
 
• mianserin
 
• trazodone
 
• amitriptyline
 
• nortriptyline
 
• imipramine
 
• trimipramine
 
• desipramine
 
• clomipramine
 
	
	
RESTRICTED
 
Restricted due to potential for QT prolongation are the following:
 
 
• citalopram
 
• escitalopram                             
 
• venlafaxine
 
 
 
	
 
• Current treatment with an antidepressant is not required. However, if the subject is taking one of the permitted antidepressants on the left, the dose must be unchanged for at least 4 weeks prior to Baseline and should be expected to remain unchanged until the subject's final visit
 
• Citalopram is restricted to a maximum dose of 20 mg/day. Escitalopram is restricted to a maximum dose of 10 mg/day. Venlafaxine is restricted to a maximum dose of 225 mg/day.
 
• Citalopram, escitalopram, and venlafaxine are prohibited in subjects with the following ECG results at Screening:                             
 
○ QTcF >425 ms, if QRS duration <120 ms
 
○ QTcF >450 ms, if QRS duration ≥120 ms
 
 
 

Medication Class	Medication a	Prohibition/restrictions
Anxiolytics	PROHIBITED 
 
• chlordiazepoxide
 
• diazepam
 
• flurazepam
 
	
 
• Prohibited at Baseline and throughout the study
 

	RESTRICTED 
 
• alprazolam
 
• clonazepam
 
• lorazepam
 
• oxazepam
 
• temazepam
 
• midazolam
 
• triazolam
 
	
 
• Short- or medium-acting benzodiazepine may be used. Reasonable efforts should be made to use minimum dose necessary for symptom management.
 
• May not be used within 12 hours prior to an assessment visit
 

Stimulants	PROHIBITED 
 
• methylphenidate
 
• modafinil
 
• armodafinil
 
	
 
• Prohibited at Baseline and throughout the study
 

Non-stimulant ADHD medications	PROHIBITED 
 
• atomoxetine
 
• guanfacine
 
	
 
• Prohibited at Baseline and throughout the study
 

Serotonin antagonists	PROHIBITED 
 
• cyproheptadine
 
• fluvoxamine
 
• mianserin
 
• mirtazapine
 
• nefazodone
 
• trazodone
 
	
 
• Prohibited throughout the study
 
• Must be discontinued 5 half-lives prior to the Baseline visit
 

Antiarrhythmic drugs	PROHIBITED 
 
• ajmaline
 
• amakalant, semantilide
 
• amiodarone
 
• bretylium
 
• disopyramide
 
• dofetilide
 
• dronedarone
 
• flecainide
 
• ibutilide
 
• procainamide
 
• propafenone
 
• quinidine
 
• sotalol, d-sotalol
 
	
 
• Prohibited at Baseline and throughout the study
 

Antimicrobials, antifungals, and antimalarials	PROHIBITED 
 
• clarithromycin
 
• erythromycin
 
• levofloxacin
 
• moxifloxacin
 
• pentamidine
 
	
 
• Clarithromycin, erythromycin, levofloxacin, moxifloxacin, and pentamidine are prohibited at study entry and throughout the study
 

Medication Class	Medication a	Prohibition/restrictions
	
RESTRICTED
 
 
• arteminol/piperaquine
 
• azithromycin
 
• bedaquiline
 
• ciprofloxacin
 
• gemifloxacin
 
• norfloxacin
 
• ofloxacin
 
• quinine
 
• roxithromycin
 
	
 
• Ciprofloxacin and azithromycin are restricted
 
• Prohibited at Baseline but may be used during the course of the study to treat a bacterial infection (e.g., urinary tract infection, respiratory infection), post-Baseline at the discretion of the Principal Investigator (PI).
 
• Arteminol/piperaquine, bedaquiline, gemifloxacin, norfloxacin, ofloxacin, quinine, and roxithromycin are only allowed under the following conditions: 
 
○ The subject has a Baseline ECG with a QTcF <425 ms OR
 
○ The subject has a QTcF <450 ms at Baseline AND QRS duration ≥120 ms
 
 
 

Herbal and nutritional supplements	
PROHIBITED
 
 
• St. John’s wart
 
• S-adenosylmethionine (SAM-E)
 
• valerian root
 
• melatonin
 
• L-tryptophan
 
	
 
• Prohibited at Baseline and throughout the study
 

a Medications within each class include but are not limited to the examples listed in this table.

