## **4 SUBJECT ELIGIBILITY AND WITHDRAWAL CRITERIA**

### **4.1 Subject Selection and Withdrawal**

To be eligible for this study, subjects must meet all of the inclusion criteria and none of the exclusion criteria.

Protocol waivers for eligibility will not be granted by the Sponsor under any circumstances. If, during the course of the study, it is discovered that the subject did not meet all eligibility criteria, she or he will be discontinued, unless the discontinuation presents an unacceptable medical risk. The justification to allow the subject to continue in the study will be made by the Sponsor, with medical input from the Investigator, and will be documented. If allowed to remain in the trial, this will be reported as a major protocol deviation and not a waiver.

Subjects who screen fail will be allowed to re-screen with the permission of the Medical Monitor, provided the screen failure was due to a temporary condition that subsequently resolved.

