### **4.2 Inclusion Criteria**

1. Is a male or female  $\geq 50$  years of age
2. Can understand and provide signed informed consent, request for medical records and/or subject privacy form if applicable according to local regulations [REDACTED]  
[REDACTED] can be reliably rated on assessment scales (in the opinion of the Investigator), and has a reliable [REDACTED] (personal friend, or professional caregiver) who can report on the subject's health-related quality of life
4. Has a clinical diagnosis of idiopathic Parkinson's disease with a minimum duration of 1 year, defined as the presence of at least three of the following cardinal features, in the absence of alternative explanations or atypical features:
  - a. rest tremor
  - b. rigidity
  - c. bradykinesia and/or akinesia

- d. postural and gait abnormalities
- 5. Meets clinical criteria for depression with Parkinson's disease as listed in the NINDS/NIMH Guidelines ([Marsh et al. 2006](#))
- 6. Has a Hamilton Depression Scale-17 item (HAM-D-17) total score  $\geq 15$  at Screening and Baseline
- 7. If currently taking an antidepressant, is being treated with only one of the following SSRI or SNRI antidepressants at a dose within the United States Food and Drug Administration (US FDA)-approved dose range. Subjects who are currently taking a second antidepressant or antidepressant augmentation agent at a sub-therapeutic dose or for an inadequate duration at Screening, and can be discontinued from this agent before the Baseline visit (in the opinion of the Investigator), may be eligible for the study.
  - a. Citalopram
  - b. Escitalopram
  - c. Paroxetine
  - d. Fluoxetine
  - e. Sertraline
  - f. Vortioxetine
  - g. Duloxetine
  - h. Venlafaxine
  - i. Desvenlafaxine
  - j. Venlafaxine XR
  - k. Vilazodone
  - l. Levomilnacipran

Current or previous treatment with an antidepressant is not required [REDACTED]  
[REDACTED] appropriate (e.g.,  
symptoms are not well controlled or the subject cannot tolerate the [REDACTED]  
[REDACTED]

- 8. If the subject is currently taking an antidepressant and has an improvement in depression of less than 75% when working at its best, as confirmed by the Massachusetts General Hospital Antidepressant Treatment Questionnaire (MGH ATRQ)
- 9. Has a Mini Mental State Exam (MMSE) score  $\geq 21$
- 10. Is on a stable dose of anti-Parkinson's medication for at least 1 month prior to Screening

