### 6.1.3 Massachusetts General Hospital Antidepressant Treatment Response Questionnaire

The MGH ATRQ (Fava and Davidson 1996; Fava 2003) is a clinician-assisted questionnaire that is to be completed only for subjects who are currently taking an antidepressant at Screening. The MGH ATRQ examines a patient's antidepressant treatment history using specific anchor points to define the adequacy of both the dose and duration of each antidepressant course, as well as the degree of symptomatic improvement obtained with each course. This validated questionnaire allows for the determination of inadequate response to antidepressant therapy (Chandler et al. 2010). If taking an approved SSRI/SNRI, subjects should be exposed to an antidepressant for at least 4 weeks at a dose appropriate for this population.

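### Appendix A ties its unchanged-dose rule for background antidepressants to a cell naming 3 of the 12 entries in Inclusion 7, so at least 8 permitted drugs have no clear dose-stability rule

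*Protocol*

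**What the plan says.** Inclusion 7 (Protocol 4.2) lets a subject stay on an antidepressant when "being treated with only one of the following SSRI or SNRI antidepressants at a dose within the United States Food and Drug Administration" approved range. It lists 12 entries, a to l. Its remark about inadequate duration concerns only a second agent that is to be stopped before Baseline.

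Inclusion 8 requires that a subject on an antidepressant "has an improvement in depression of less than 75% when working at its best", confirmed by the MGH ATRQ. Section 6.1.3 adds that, on an approved SSRI/SNRI, "subjects should be exposed to an antidepressant for at least 4 weeks at a dose appropriate for this population".

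Dose stability appears in Appendix A, in the restricted part of the antidepressant row. Its left cell is headed "Restricted due to potential for QT prolongation are the following" and lists citalopram, escitalopram and venlafaxine. The right cell says that if the subject takes "one of the permitted antidepressants on the left, the dose must be unchanged for at least 4 weeks prior to Baseline", and that no change is expected up to the final visit. Further bullets give dose caps and ECG limits for the same three drugs. A table note says "Medications within each class include but are not limited to the examples listed in this table".

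Section 4.5 applies the Appendix A restrictions from Screening to end of treatment. The primary hypothesis (Protocol 9.8.1, SAP 13.1) is that mean HAMD-17 change at Week 8 is zero, in one arm.

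**The concern.** The stability rule points to a list drawn up for another purpose, cardiac safety. A site following the table would hold a citalopram dose fixed. For sertraline or duloxetine it would find no instruction in the visible text, either for the weeks before Baseline or for the treatment period.

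This matters because there is no control arm. If a background dose rises shortly before Baseline or on study, any improvement that follows is counted in the change attributed to pimavanserin. A dose reduction would act the other way. Only adjunctive subjects are exposed to this. They are also a prespecified subgroup (Protocol 9.6, SAP 12.5), so any distortion concentrates in that estimate.

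**Working it through.** **1. Count.** Inclusion 7 lists citalopram, escitalopram, paroxetine, fluoxetine, sertraline, vortioxetine, duloxetine, venlafaxine, desvenlafaxine, venlafaxine XR, vilazodone and levomilnacipran: 12 entries. Appendix A's left cell names 3.

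- XR counted separately: 3/12 = 25% named; 12 − 3 = 9 (75%) not named.
- XR counted as venlafaxine: 4/12 = 33% named; 12 − 4 = 8 (67%) not named.

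The eight unnamed on either count are paroxetine, fluoxetine, sertraline, vortioxetine, duloxetine, desvenlafaxine, vilazodone and levomilnacipran.

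**2. Does other visible text close the gap?**

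| Text | What it controls | Dose change before Baseline | Dose change on study |
|---|---|---|---|
| Inclusion 7 | Drug and dose range | No | No |
| Inclusion 8 with ATRQ | Improvement; ATRQ rates adequacy of dose and duration at Screening | Partly, up to Screening | No |
| Section 6.1.3 | At least 4 weeks' exposure at an appropriate dose | Recent start yes; later change of dose no | No |
| Inclusion 10 | Anti-Parkinson's drugs only | Not applicable | Not applicable |
| Appendix A stability rule | Drugs in the left cell | Yes, for those named | Expected stable, for those named |

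Screening falls 1 to 21 days before Baseline, so the ATRQ cannot see a change made between the two visits.

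**3. The plan's own sample size.** For a two-sided paired t-test with mean change 3, SD 6 and alpha 0.05, noncentral-t power is 0.795 at n = 33 and 0.808 at n = 34. The stated 34 is reproduced. Allowing for 15% non-evaluable, 34/0.85 = 40, also as stated.

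**4. Scale of a possible bias.** The documents do not say how many subjects take each drug or how much a dose change would move HAMD-17. Assume 1 to 4 points per affected subject.

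- Shift in a 34-subject mean per affected subject: 1/34 = 0.03 to 4/34 = 0.12 points.
- Smallest observed mean change at which the planned t-test rejects: SE = 6/√34 = 1.029; t(0.975, 33 df) = 2.035; 2.035 × 1.029 = 2.09 points.
- Subjects needed to reach that from this source alone, at 4 points each: 2.09 × 34/4 = 17.8, so 18 of 34.
- At 2 points each, with all 34 affected: 34 × 2/34 = 2.00, still below 2.09.

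The primary analysis is an MMRM, so 2.09 is a yardstick and not its exact threshold.

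**5. Adjunctive subgroup.** Its size is not given. Per affected subject, the shift in its mean is:

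- 10 adjunctive subjects (assumed): 1/10 = 0.10 to 4/10 = 0.40 points.
- 17 (assumed, half of 34): 1/17 = 0.06 to 4/17 = 0.24.
- 24 (assumed): 1/24 = 0.04 to 4/24 = 0.17.

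**The case against.** The strongest reply is that this is loose drafting and the intent is plain. The table's drugs are declared to be examples. The stability bullet opens generally, by noting that no antidepressant is required, and speaks of permitted antidepressants; the cap and ECG bullets name their three drugs. Appendix A also sends questions to the Medical Monitor.

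This holds as evidence of intent, but it does not settle scope. The note extends examples within a class, and this row's class is antidepressants *other than* background therapy. Reading sertraline or duloxetine into the left cell would label them QT-restricted, whereas Exclusion 5 singles out the same three drugs. Where one drug alone was meant to carry such a rule, the protocol names it: "Valproate may be used if dose unchanged for at least 4 weeks prior to Baseline".

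A second reply is that recent starts are already handled. This largely stands. Section 6.1.3 covers any approved SSRI/SNRI, the ATRQ rates adequacy of dose and duration, and SAP 8.2 lists whether the dose was taken for at least 4 weeks. A reader might infer that the *should* in 6.1.3, set against "To be eligible for this study, subjects must meet all of the inclusion criteria and none of the exclusion criteria", makes that expectation optional. The documents do not support leaning on the word. The protocol uses *should* for operative duties elsewhere: following the appendices (4.5), withdrawing a subject at suicide risk (6.3.6) and rating UPDRS in the on state (6.3.7).

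A third reply is that text is missing. Parts of Sections 4.4 and 4.5 are redacted or absent, so the gap can be asserted for the visible text only.

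**Conclusion.** The point holds in a narrow form. In the visible text, the unchanged-dose rule clearly reaches 3 of 12 permitted entries, or 4 with venlafaxine XR. Dose changes of at least 8 other permitted drugs, shortly before Baseline and mainly during the 8 weeks, fall under no clear rule.

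Two stronger readings should be resisted. One is that the sponsor meant to leave the other drugs free to be titrated; the wording suggests the opposite. The other is that this could produce a positive primary result. Under the assumed effects that would take 18 of 34 subjects at 4 points each, and it is out of reach at 2 points or less.

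The bias is probably small, could run in either direction, and matters mainly for the adjunctive estimate. Monotherapy subjects are unaffected and are analysed separately (SAP 12.5). The size rests on an assumed 1 to 4 points and on unknown numbers of subjects per drug. The single-arm design stays confounded whether or not this is corrected. This is a cheap improvement that removes one avoidable alternative explanation.

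**What to change.** In the stability sentence of Appendix A, replace the reference to the drugs on the left with *any antidepressant permitted by Inclusion 7*. Keep the 4-week anchor to Baseline and the expectation of no change to the final visit. Leave the QT dose caps and ECG limits on citalopram, escitalopram and venlafaxine only. Inclusion 7, Inclusion 8, Section 6.1.3, the SAP and the primary model need no change.

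The cost is one edited sentence in a short amendment with IRB/EC approval (Protocol 10.7), and slightly slower entry for a few adjunctive candidates who must wait or re-screen. Section 4.5 still lets the investigator adjust medication to manage an adverse event. Subjects already enrolled came in under the present wording. The SAP already provides background-treatment duration and the 4-week item (8.2) and tabulates background drugs by dose level (10), which helps to describe them.
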